6.2.1.5 Procedures for Reporting Adverse Events

All AEs and their outcomes must be reported to Ora, the study sponsor, and the IRB/IEC as required by the IRB/IEC, federal, state, or local regulations and governing health authorities and recorded on the appropriate CRF.

6.2.1.6 Reporting a Suspected Unexpected Adverse Reaction

[figure not shown]
All AEs that are ‘suspected’ and ‘unexpected’ are to be reported to Ora within 24 hours. Ora and the Sponsor will immediately conduct an evaluation of the reported event. The results of the evaluation will be reported to the IRB within 10 days of Ora and/or the Sponsor becoming aware of the event. Events must be reported to the study sponsor and the IRB/IEC as required by the IRB/IEC, federal, state, or local regulations and governing health authorities.

6.2.1.7 Reporting a Serious Adverse Event

To ensure subject safety, all SAEs, regardless of relationship to the investigational product, must be immediately reported. All information relevant to the SAE must be recorded on the appropriate case report forms. The investigator is obligated to pursue and obtain information requested by Ora and/or the sponsor in addition to that information reported on the case report form. All subjects experiencing a SAE must be followed up and the outcome reported.

In the event of a SAE, the investigator must notify Ora and the sponsor within 24 hours; obtain and maintain in his/her files all pertinent medical records, information, and medical judgments from colleagues who assisted in the treatment and follow-up of the subject; provide Ora and the study sponsor with a complete case history, which includes a statement as to whether the event was or was not suspected to be related to the use of the investigational product; and inform the IRB of the SAE within their guidelines for reporting SAEs.

Contact information (SAEs):

6.2.1.8 Type and Duration of the Follow-up of Subjects after Adverse Events

All AEs irrespective of the suspected causality will be monitored until the AE has resolved or until the end of the study (Week 24), unless the subject is lost to follow-up or withdraws consent or the subject died prior to the end of the study. All SAEs, irrespective of the suspected causality, will be monitored until the SAE has resolved or until the subject is lost to follow-up or the subject has died.

6.2.1.9 Pregnancy

The Sponsor has a responsibility to monitor the outcome of pregnancies where there has been maternal exposure to the study drug.

Pregnancy alone is not regarded as an AE unless there is a suspicion that the study drug may have interfered with the effectiveness of a contraceptive medication.

Elective abortions without complications should not be handled as AEs, unless they were therapeutic abortions (see below). Hospitalization for normal delivery of a healthy newborn should not be considered a SAE.

All pregnancies must be reported by the Investigator to Ora/Sponsor on the initial pregnancy report form within 30 days after becoming aware of the pregnancy. The Investigator must follow-up and document the course and the outcome of all pregnancies even if the patient was discontinued from the study or if the study has finished.

All outcomes of pregnancy must be reported by the Investigator to Ora on the pregnancy outcome report form within 30 days of becoming aware of the normal delivery or elective abortion.

Any SAE that occurs during pregnancy (including SAEs occurring after last administration of study drug) must be recorded on the SAE report form (e.g., maternal serious complications, spontaneous or therapeutic abortion, ectopic pregnancy, stillbirth, neonatal death, congenital anomaly, or birth defect) and reported within 24 hours in accordance with the procedure for reporting SAEs.

If a female partner of a male study patient who has been exposed to the study drug becomes pregnant, the pregnancy and outcome of pregnancy should be monitored according to the same guidelines as for female subjects who become pregnant during the study.

6.2.2 Laboratory Variables

Laboratory assessments will be performed by a central laboratory, as identified in the List of Study Personnel. Before starting the study, the central lab will supply a list of the normal ranges and units of measurement.

Blood samples should be taken using standard venipuncture techniques. A lab manual will be provided by the central laboratory; this will contain very detailed instructions for collection, storage, and shipment of samples (e.g., what kind of tubes, what kind of sample preparation, mailing addresses, etc.).

The following laboratory variables will be determined in accordance with the Schedule of Procedures (Table 2):

Table 1: Laboratory Assessments

Hematology:	Erythrocytes MCV MCH Neutrophils Eosinophils Basophils Lymphocytes Monocytes Platelets Leukocytes Hemoglobin Hematocrit	Urinalysis:	pH Protein Glucose Ketone Bilirubin Blood Nitrite Microalbuminemia Proteinuria
Clinical chemistry:	HgA1c Creatinine Glucose Triglycerides Urea Uric acid Bilirubin Cholesterol	Liver enzymes:	Alkaline phosphatase AST ALT GGT
Electrolytes:	Sodium Potassium		
Urine pregnancy test:	In women with childbearing potential		
Abbreviations: ALT = Alanine aminotransferase; AST = Aspartate aminotransferase; GGT = Gamma glutamyl transferase; HgA1c = Glycosylated hemoglobin; HMWK = high molecular weight kininogen; MCH = mean corpuscular hemoglobin; MCV = mean corpuscular volume; pH = potential hydrogen; PKal = plasma kallikrein.			

The Investigator must review screening laboratory results for subject eligibility prior to enrolling.

Laboratory tests can be repeated earlier than the next scheduled consecutive study visit at the Investigator's discretion and any associated safety issue should be followed up as per the Investigator's clinical judgement until resolution/stabilization.

Laboratory data will be electronically transferred to the clinical database at specified time points during the study.

6.3 Methods of Assessment

The following assessments will be conducted and recorded in the eCRF. The Schedule of Procedures and Procedures by Visit can be found in Sections 7.1 and 7.2, respectively.

6.3.1 Subject Demography

Subject demography will be performed at the Screening visit and consists of:

- Date of birth;
- Height;
- Weight;
- Race and ethnicity;
- Gender
- Iris color

6.3.2 Medical and Ocular History

For the documentation of the medical history, any relevant previous and concurrent diseases will be documented.

The medical history will be obtained by interviewing the subject or by inspecting relevant medical records.

For coding of medical history, see Section 9.4.

6.3.2.1 DME Disease History

DME disease history will be recorded at the Screening visit. For disease history the following will be documented:

- Date of first diagnosis of DME in the study eye
- Date and details of the first anti-VEGF injection
- Dates and details of the last three anti-VEGF injections
 - BCVA score or Snellen equivalent of each VA assessment in the study eye beginning with the VA assessment immediately prior to the last three anti-VEGF injections
 - CST from each OCT assessment in the study eye beginning with the OCT assessment immediately prior to the last three anti-VEGF injections
- Estimate or actual total number of anti-VEGF injections
- Date of last IVT steroid injection (if any)
- Estimate or actual total number of IVT steroid injections (if any)

The Investigator's assessment of the subject's response to anti-VEGF treatment after the last 3 IVT injections compared to baseline will be recorded using the following scales (baseline is defined as the status of edema and vision immediately prior to the first of the 3 injections):

Edema:

- Satisfactory response – Absence of intraretinal/subretinal fluid;
- Partial response 1 – Significant reduction of intraretinal/subretinal fluid;
- Partial response 2 - Little or some reduction (~20%) of intraretinal/subretinal fluid;
- No response – No reduction or worsening of intraretinal/subretinal fluid.

Vision:

- No change in or worsening of BCVA
- Gain of 1-4 letters
- Gain of 5 to 9 letters
- Gain 10 to 14 letters
- Gain of ≥ 15 letters

6.3.3 Previous and Concomitant Medications

Previous and concomitant medication will be documented as described in Section 5.7.

6.3.4 Vital Signs

The following vital signs will be assessed at rest (5 minutes in a supine position) in accordance with the Schedule of Procedures (Table 2). The same equipment for each vital sign evaluation should be used on given patient for all study visits. Vital signs should be conducted prior to study drug administration and approximately 30 minutes post-study drug administration on applicable visits.

- Blood pressure (SBP and DBP; mmHg);
- Pulse rate (beats per minute);
- Body temperature ($^{\circ}\text{C}$);
- Respiration rate (breaths per minute).

6.3.5 Physical Examinations

Physical examinations will be performed in accordance with the Schedule of Procedures (Table 2). The physical examination should be symptom directed and include the following body systems: general appearance, skin, lymphatic, head and neck, ears, nose and throat, chest and lungs, cardiovascular, abdomen, extremities, musculoskeletal and neuromuscular.

6.3.6 Safety Laboratory Assessments

Laboratory assessments will be conducted in accordance with Section 6.2.2. The central laboratory will provide a lab manual with detailed procedures. Safety labs should be collected prior to study drug administration on applicable visits.

6.3.7 Ophthalmic Assessments

Ophthalmic findings will be performed in accordance with the Schedule of Procedures (Table 2). All ophthalmic assessments will be conducted on both eyes except fundus photography which will be taken in both eyes at the Screening visit and only in the study eye at subsequent visits.

Best Corrected Visual Acuity Early Treatment Diabetic Retinopathy Study (BCVA ETDRS):

BCVA of both eyes will be assessed using the ETDRS protocol. Detailed instructions for performing manifest refraction and BCVA will be provided in the study-specific BCVA manual. BCVA should be performed prior to all other ophthalmic assessments at all visits.

Slit Lamp Biomicroscopy:

The eyelids, cornea, conjunctiva, anterior chamber, iris/pupil and lens should be evaluated. Findings will be graded as normal, abnormal non-clinically significant, or abnormal clinically significant. Slit lamp biomicroscopy will be performed on both eyes and should be conducted prior to study drug administration on applicable visits.

Intraocular Pressure (IOP):

IOP will be assessed in both eyes at all study visits. IOP will be assessed with either applanation tonometry or tonopen; the method should be consistent throughout the study. IOP will be assessed at both pre- and post- injection at visits with study drug administrations. Pre-injection IOP must be performed prior to dilation. Post-injection IOP should be assessed within 60 minutes after study drug or sham administration and should be assessed by someone who is unmasked.

Dilated Indirect Ophthalmoscopy:

The vitreous, macula, choroid, optic nerve, and retina of both eyes will be assessed. Findings will be graded as normal, abnormal non-clinically significant, or abnormal clinically significant. The dilated indirect ophthalmoscopy will be performed on both eyes and should be conducted prior to study drug administration on applicable visits.

Fundus Photography:

Color fundus photographs will be taken in both eyes at Screening and in the study eye at subsequent visits to evaluate retinal anatomy and grade DRSS. Photographs will be transferred to the CIRC for independent analysis. Detailed instructions for imaging and data transfers will be provided in the study-specific Image Acquisition and Submission Protocol. Fundus photography should be conducted prior to study drug administration on applicable visits.

Spectral Domain Optical Coherence Tomography (SD-OCT):

SD-OCT will be utilized to assess retinal thickness. All sites will be required to use a Heidelberg Spectralis SD-OCT. OCT imaging data will be transmitted to a Central CIRC for independent analysis. Detailed instructions for imaging and data transfers will be provided in the study-specific Image Acquisition and Submission Protocol. SD-OCT should be conducted prior to study drug administration on applicable visits.

[REDACTED]

7 STUDY CONDUCT

7.1 Schedule of Procedures

A list of procedures to be conducted, by visit, is described in [Table 2](#).

Visits should occur on:

- Day 1 and Weeks 4, 8, and 12 during the Treatment Phase;
- Weeks 16, 20, and 24 during Follow-up Phase.

Changes to the dosing schedule outside of the specified windows must be discussed with the Medical Monitor. All times should be recorded using the 24-hour clock (e.g., 23:20, not 11:20 pm).

Table 2: Schedule of Procedures

Clinic Visit (V)	Visit 1 Screen	Visit 2	Call	Visit 3	Call	Visit 4	Call	Visit 5	Call	Visit 6	Visit 7	Visit 8/ ED Visit
Day (D)	Week -4 to Day -1	Day 1	Visit 2 +1 day	Week 4 (-3 to +7 days)	Visit 3 +1 day	Week 8 (-3 to +7 days)	Visit 4 +1 day	Week 12 (-3 to +7 days)	Visit 5 +1 Day	Week 16 (±1 Week)	Week 20 (±1 Week)	Week 24 (±1 Week)
Informed Consent	X											
Eligibility Assessment	X	X										
Demographics	X											
Concomitant Medications	X	X	X	X	X	X	X	X	X	X	X	X
Physical Examination (height, weight, BMI)	X											
Medical/Ocular History	X	X	X	X	X	X	X	X	X	X	X	X
Vital Signs ^a	X	X		X		X		X		X		
Safety Laboratory ^b	X	X		X		X		X		X		
██████████		X										
Study Drug Administration (KVD001 Injection) or Sham Procedure		X		X		X		X				
Urine Pregnancy Test (women)	X	X		X		X		X		X		
Adverse Events ^c	X	X	X	X	X	X	X	X	X	X	X	X

Table 2 Schedule of Procedures (Cont'd)

Clinic Visit (V)	Visit 1 Screen		Visit 2		Call	Visit 3		Call	Visit 4		Call	Visit 5		Call	Visit 6		Visit 7		Visit 8/ ED Visit	
Day (D)	Week -4 to Day -1		Day 1		Visit 2 +1 day	Week 4 (-3 to +7 days)		Visit 3 +1 day	Week 8 (-3 to +7 days)		Visit 4 +1 day	Week 12 (-3 to +7 days)		Visit 5 +1 day	Week 16 (±1 Week)		Week 20 (±1 Week)		Week 24 (±1 Week)	
OCULAR	SE	FE	SE	FE		SE	FE		SE	FE		SE	FE		SE	FE	SE	FE	SE	FE
BCVA ^{d,e}	X	X	X	X		X	X		X	X		X	X		X	X	X	X	X	X
Slit Lamp Biomicroscopy ^d	X	X	X	X		X	X		X	X		X	X		X	X	X	X	X	X
Dilated Indirect Ophthalmoscopy ^d	X	X	X	X		X	X		X	X		X	X		X	X	X	X	X	X
IOP ^f	X	X	X	X		X	X		X	X		X	X		X	X	X	X	X	X
Fundus Photography ^d	X	X	X			X			X			X			X		X		X	
SD-OCT ^d	X	X	X	X		X	X		X	X		X	X		X	X	X	X	X	X

Abbreviations: AEs = Adverse events; BCVA = Best corrected visual acuity; BMI = Body mass index; ED Visit = Early discontinuation visit; FE = Fellow eye; IOP = Intraocular pressure; SD-OCT = Spectral domain optical coherence tomography; SE = Study eye.

^a Vital signs include pulse rate, respiratory rate, systolic and diastolic blood pressure, and temperature. Vital signs will be taken prior to and approximately 30 minutes after study drug

^b Safety labs are detailed in Section 6.2.2.

^c AEs to be recorded from time of signing of informed consent form

^d Procedure will be performed prior to study drug administration or sham procedure on applicable visits.

^e BCVA will be performed prior to all other ophthalmic procedures.

^f IOP will be taken prior to and within 60 minutes following study drug administration or sham procedure at applicable visits. Pre-study drug administration IOP must be performed prior to dilation. Post study-drug administration IOP must be performed by unmasked personnel.

7.2 Procedures by Visit

Prior to any study activities, subjects will be asked to read and sign an ICF that has been approved by an Independent IEC/IRB and the Sponsor and which complies with regulatory requirements.

All times should be recorded using the 24-hour clock (e.g., 23:20, not 11:20 pm).

Ophthalmic procedures are proposed to occur in the following order at Visits 2-5:

- BCVA (must be performed prior to all other ophthalmic procedures)
- Slit lamp biomicroscopy
- Pre-Injection IOP/IOP at visits with no study drug administration (must be done prior to dilation)
- Dilated indirect ophthalmoscopy
- Fundus photography
- SD-OCT
- Intravitreal injection
- Post-Injection IOP

7.2.1 Screening Phase (Weeks -4 to Day -1 [Visit 1])

Subjects will undergo screening during a visit that can occur up to 4 weeks prior to the Day 1 Visit. Following full discussion of the study and the signing of ICF, a screening subject ID number will be assigned. All subjects will be assessed for eligibility against the inclusion and exclusion criteria.

The following screening and baseline assessments will be performed:

- Obtain subject's full medical history, including ophthalmic ocular history with DME disease history, concomitant illnesses/diseases and medications, therapies and supplements taken within the past 3 months, previous participation in interventional clinical studies in the past three months;
- Record demographic information including race, ethnicity and date of birth;
- Conduct the following ophthalmic measurements and examinations in both study eye and fellow eye in accordance with procedures as described in Section 6.3.7;
 - BCVA;
 - Slit lamp biomicroscopy;
 - IOP (prior to dilation);
 - Dilated indirect ophthalmoscopy;
 - Fundus photography;
 - SD-OCT;
- Collect blood and urine samples per Section 6.3;
- Perform measurements of height (meters [m], without shoes) and weight (kilogram [kg], without shoes or overcoat). Calculation of body mass index (BMI) will be automated in the database;
- Vital signs (Blood pressure [BP], PR, respiratory rate, and body temperature [°C])
 - BP and PR will be recorded after subject has been supine for 5 minutes;
- Urine pregnancy test (women of childbearing potential);

- Perform eligibility check, evaluating all results of the screening assessment results against the inclusion and exclusion criteria;
- All AEs reported after signing of the ICF will be recorded;
- Review the study procedures and study visit schedule with the subject.

7.2.2 Treatment Phase

7.2.2.1 Day 1 and Weeks 4, 8, and 12 (Visits 2, 3, 4, and 5)

Visits are to occur within -3 to +7 days for Weeks 4, 8, and 12. Subjects should attend Clinic Visit 2 within 4 weeks of screening.

The following assessments will be performed:

- Reconfirm eligibility (Day 1 only);
- Collect blood and urine samples per Section 6.2.2;
- [REDACTED]
- Collect any changes to medical or ocular history;
- Record any AEs;
- Record any change to the concomitant medication;
- Urine pregnancy test (women of childbearing potential);
- Vital signs (BP, PR, respiratory rate, and body temperature [°C]) – BP and PR will be recorded after subject has been supine for 5 minutes. Vitals signs will be collected prior to and approximately 30 minutes after study drug administration or sham procedure;
- Conduct the following ophthalmic measurements and examinations in both study eye and fellow eye (except fundus photograph) in accordance with procedures as described in Section 6.3.7;
 - BCVA;
 - Slit lamp biomicroscopy;
- IOP will be collected performed prior to and within 60 minutes (Post study-drug administration IOP must be performed by unmasked personnel) after study drug administration or sham procedure. Pre-study drug administration IOP must be conducted prior to dilation;
 - Dilated indirect ophthalmoscopy;
 - Fundus photography (SE only);
 - SD-OCT;
- Administer the study drug administration or sham procedure to the study eye.

7.2.2.2 Post-treatment Follow-up Call

Approximately twenty-four (24) hours after each study drug administration or sham procedure on Day 1 and Weeks 4, 8, and 12), subjects will be contacted by telephone to evaluate any reported AEs and changes in concomitant medications. In the event of any reported AEs, the subjects will return to the clinic for assessment.

7.2.3 Follow-up Phase

Following Week 12 (Visit 5) of study drug administration or sham procedure, subjects will be followed up monthly at the clinic for 12 weeks (Weeks 16, 20, and 24 [Visits 6, 7, and 8, respectively]).

7.2.3.1 Weeks 16, 20, and 24 (Visits 6, 7, and 8)

Visits are to occur within ± 1 week of the target visit date. At the visit the following procedures will be conducted:

- Collect blood and urine samples per section 6.2.2 (Week 16 only);
- Collect any changes to medical or ocular history;
- Record any AEs;
- Record any change to the concomitant medication;
- Urine pregnancy test (women of childbearing potential) (Week 16 only);
- Vital signs (BP, PR, respiratory rate, and body temperature [$^{\circ}$ C]) – BP and PR will be recorded after subject has been supine for 5 minutes (Week 16 only);
- Conduct the following ophthalmic measurements and examinations in both study eye and fellow eye in accordance with procedures as described in Section 6.3.7;
 - BCVA;
 - Slit lamp examination biomicroscopy;
 - IOP (prior to dilation);
 - Dilated indirect ophthalmoscopy;
 - Fundus photography (SE only);
 - SD-OCT;

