2.2 Secondary Objective(s)

To evaluate the local and systemic safety and tolerability of monthly dosing of KVD001 Injection in subjects with ciDME who have had prior anti-VEGF treatment.

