7.2.4 Early Discontinuation Visit

If any subject discontinues the trial early, every effort should be made to complete the Week 24/early discontinuation (ED) evaluations as soon as possible and, whenever possible, prior to starting any new medication or treatment (including rescue treatment). All attempts will be made to not discontinue the subject unless necessary.

If a study subject completes an early discontinuation evaluation for the purpose of receiving rescue treatment, then the medications used as rescue treatment will be detailed in the respective concomitant medications section of the study's EDC system.

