8.4 Data Analysis Conventions

All data analysis will be performed [REDACTED]. The final analysis will be performed after the study is completed and the database has been locked and released for unmasking. Statistical programming and analyses will be performed using SAS® Version 9.4 or higher.

Quantitative variables will be summarized using descriptive statistics including the number of observations (n), mean, SD, median, interquartile range (IQR), minimum, and maximum values. Means, medians, and confidence intervals (CIs) will be reported based on the level of precision for each variable. Summaries for discrete variables will include frequency counts and percentages. All percentages will be rounded to one decimal place (i.e., XX.X%). Change from baseline will be calculated as post-baseline value minus baseline value.

All efficacy analyses will be two-sided at a significance level of 0.05. The CIs for differences between treatment groups will be two-sided at 95% confidence. All p-values will be rounded to four decimal places; p-values less than 0.0001 will be presented as “<0.0001”; p-values greater than 0.9999 will be presented as “>0.9999.”

Extra assessments (i.e., unscheduled laboratory data or vital signs associated with non-protocol clinical visits or obtained in the course of investigating or managing AEs) will be included in listings, but not summaries. If more than one laboratory value is available for a given visit, the first valid observation will be used in summaries and all observations will be presented in listings. If the relative time is indeterminable, then the average of values at that visit will be used. It is noted that invalid laboratory data may not be used (from hemolyzed samples, mishandled samples, quantity not sufficient, or other conditions that would render values invalid).

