14.10 Laboratory Assessments

Laboratory assay results include hematology, blood chemistry (clinical chemistry, liver enzymes, electrolytes), and urinalysis. Laboratory data will be obtained at all scheduled visits except Visit 7 (Week 20) and Visit 8 (Week 24). Each of the continuous parameters will be summarized using continuous descriptive statistics for each treatment group at each visit. Changes from baseline will also be summarized for each treatment group. Each categorical parameter will be summarized using frequency counts and percentages for each treatment group and for all subjects.

Laboratory data will be classified as high, low or normal. High and low values will be classified as clinically significant or not clinically significant. The high/low criteria will be determined based on the reference ranges provided by the laboratory. A shift table of the changes from baseline to each post-baseline visit will be presented for hematology, blood chemistry (clinical chemistry, liver enzymes, electrolytes), and urinalysis. Shift tables will present a crosstabulation of baseline categories versus post baseline categories for each post-baseline visit as well as shifts from baseline to post-baseline high and post-baseline low.

Listing of blood chemistry (clinical chemistry, liver enzymes, electrolytes), hematology and urinalysis will be presented.

All laboratory values will be presented using SI units.

16. Changes from Protocol-Stated Analyses

The definition of the FAS population has been updated to exclude subjects who did not receive at least 1 dose of study treatment in **Section 7.1**.

The definition of the PPS population has been updated to exclude subjects who did not receive all four doses of study treatment, have a missing Week 16 BCVA result, or discontinued prior to Week 16 for any reason in **Section 7.2**.

The definition of prior medications has been extended to include medications prior to Day 1 in **Section 11.2**.

Between KVD001 Injection dose comparisons were added in **Section 2.4**, **Section 13.1**, **Section 13.2**, and **Section 13.3**.

Clopper-Pearson CIs instead of asymptotic normal CIs are used for the proportion-based analyses in **Section 13.3**.

The proportion of SEs with any BCVA letter loss from baseline has been added as an exploratory efficacy endpoint in **Section 13.3**.

17. References

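### The early discontinuation visit copies Week 24, so a subject whose next visit after a dose is an ED visit before Week 16 has no scheduled labs or pregnancy test after that dose, and no vital signs after the 30-minute reading

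*Protocol*

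**What the plan says.** The secondary objective in Protocol 2.2 covers systemic as well as local safety: "To evaluate the local and systemic safety and tolerability of monthly dosing of KVD001 Injection in subjects with ciDME". Protocol 3.2.2 names laboratory results and vital signs among the safety endpoints, beside adverse events.

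For a subject who leaves early, Protocol 7.2.4 says "every effort should be made to complete the Week 24/early discontinuation (ED) evaluations as soon as possible". Protocol Table 2 and SAP Appendix A use a single column for Visit 8 and the ED visit.

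Protocol 7.2.3.1 restricts three items in the follow-up phase:
- labs: "Collect blood and urine samples per section 6.2.2 (Week 16 only")
- pregnancy test: "Urine pregnancy test (women of childbearing potential) (Week 16 only")
- vital signs: "BP and PR will be recorded after subject has been supine for 5 minutes (Week 16 only")

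In both schedule tables these three rows are last marked at Visit 6 (Week 16). SAP 14.10 agrees: "Laboratory data will be obtained at all scheduled visits except Visit 7 (Week 20) and Visit 8 (Week 24"). SAP 14.8 says the same of vital signs. Neither section makes an exception for an ED visit.

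At dosing visits, Protocol 6.3.6 sets the order: "Safety labs should be collected prior to study drug administration on applicable visits". Protocol 7.2.2.1 schedules vital signs before the dose and about 30 minutes after it. Protocol 7.2.2.2 schedules a telephone call at about 24 hours for adverse events and concomitant medication.

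**The concern.** Leaving these tests out at Week 24 is reasonable for a completer, who had them at Week 16, four weeks after the last dose. The same list is then applied to someone who leaves during treatment and never reaches Week 16. Because labs precede each dose, the effect of a dose on laboratory values is read at the next visit. If that visit is an ED visit, it is not read at all.

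This group is not a random sample of those dosed. Adverse events are a listed reason for withdrawal in Protocol 4.3, and Protocol 5.8 discontinues anyone who receives rescue in the study eye. The laboratory and vital-sign part of the systemic safety objective would be thinnest in subjects who did not stay the course. A woman of childbearing potential who leaves during treatment would also have no scheduled exit pregnancy test, although Protocol 6.2.1.9 accepts responsibility for monitoring pregnancies after exposure.

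**Working it through.** The plan states no figure on this point, so there is none to reproduce. The check sets the schedule against the ED definition.

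**1. Scheduled systemic assessments after the last dose.** The inputs are Protocol Table 2, 6.3.6, 7.2.2.1, 7.2.2.2, 7.2.3.1 and 7.2.4.

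| Assessment | Next visit is an ED visit before Week 16 | Completer, after the Week 12 dose |
|---|---|---|
| Safety labs | 0 | 1 (Week 16) |
| Urine pregnancy test | 0 | 1 (Week 16) |
| Vital signs | 1 (about 30 minutes after the dose) | 2 (30 minutes; Week 16) |
| Adverse-event enquiry | 2 (24-hour call; ED visit) | 4 (call; Weeks 16, 20, 24) |

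The middle column is the same whether the last dose was on Day 1 or at Week 4, 8 or 12.

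**2. Two cases.**
- Dosed at Week 8, ED visit at Week 10: the last labs were drawn before the Week 8 dose. They reflect the first two doses and not the third.
- Dosed on Day 1, ED visit before Week 4: no post-baseline labs, and vital signs only at about 30 minutes.

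**3. Number affected.** Planned KVD001 subjects: 2 × 41 = 82. Assumed exit before Week 16 of 10% to 20%: 0.10 × 82 = 8.2 and 0.20 × 82 = 16.4, so about 8 to 16. This is an upper limit. A subject who attends a Week 4, 8 or 12 visit and leaves from there undosed can have the labs, pregnancy test and vital signs scheduled for that visit.

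**4. Would the SAP use such values if they were collected?** SAP 3.2, Table 1 maps an ED visit to a scheduled visit. Where both fall on the same visit name, it keeps the one closest to the planned day.
- Week 8 has planned day 56 and window 43–70. With the dosing visit on Day 56 and the ED visit on Day 70, the distances are |56 − 56| = 0 and |70 − 56| = 14, so the dosing-visit value is kept and the ED value is not.
- If the ED visit is on Day 71, it maps to Week 12 (71–98). There is no competing visit, and the ED value is used.
- Day 1 has no window and Week 4 starts at Day 15, so an ED visit on Days 2 to 14 maps to no visit.

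Separately, SAP 8.4 takes the first valid laboratory value when a visit has more than one, which here would be the pre-dose value. Collecting the data is therefore not enough. The SAP also has to say where the values go.

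**The case against.** The strongest reply is that the gap is narrow and partly covered elsewhere. A reader might infer that early leavers give no systemic safety data at all after their last dose. The documents do not support that. Vital signs are scheduled about 30 minutes after every dose, and adverse events, the first-listed safety endpoint, are sought at the 24-hour call and again at the ED visit. Leavers with two or more doses also keep the post-baseline labs drawn before their later doses. That part of the reply stands.

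It is also fair that Protocol 4.3.1 follows a subject withdrawn for an adverse event until it resolves, is stable or is clearly unrelated, that 6.2.2 allows repeat labs at the investigator's discretion, and that 6.2.1.9 requires pregnancies to be followed even after discontinuation. Under Protocol 4.3 a subject may stop dosing without leaving the study, and such a subject can still have the Week 16 tests. These provisions soften the gap but do not close it: none schedules a lab, vital sign or pregnancy test at exit.

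A reader might also infer that labs taken at an ED visit are certain to be left out of the tables, because SAP 8.4 says extra assessments "will be included in listings, but not summaries". That is not certain. The rule concerns unscheduled data from non-protocol visits or from adverse-event work-up. An ED visit is a protocol visit, and SAP 3.2 windows it to a scheduled one. What can be said is that the handling is unclear for labs and vital signs that the schedule does not call for.

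Finally, the protocol and SAP agree with each other here, and parts of the background and benefit-risk text are redacted. This is a design choice that can be improved, not a contradiction.

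**Conclusion.** The point holds in limited form. For a subject whose next visit after a dose is an ED visit before Week 16, both documents leave no scheduled labs or pregnancy test after that dose and no vital signs after the same-day reading. This follows directly from the schedule and needs no assumption.

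The size does need one: at most about 8 to 16 of 82 KVD001 subjects, if 10% to 20% leave before Week 16. Neither document gives a dropout rate, nor how many leavers would leave for an adverse event, so the strength of any selection is unknown.

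A reader might go on to infer that the trial's ability to rule out a systemic event rate is weakened in proportion to these numbers. That does not follow. SAP 14 summarises adverse events in the safety set, which is everyone dosed, so early leavers stay in that denominator. The loss is in laboratory values, late vital signs and the exit pregnancy test. It is worth correcting because the correction is cheap, not because the safety analysis fails without it.

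**What to change.** **Protocol Table 2, 7.2.3.1 and 7.2.4, and SAP Appendix A:** state that an ED visit held before the Week 16 visit also includes the safety labs of Protocol 6.2.2, vital signs and, for women of childbearing potential, the urine pregnancy test.

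**SAP 14.8 and 14.10:** state that these ED values count as post-baseline in the summaries already planned, namely the maximum and minimum post-baseline vital signs and the shifts to post-baseline high and low for labs. Say that this applies even where the closest-to-planned-day rule of SAP 3.2 or the first-valid-value rule of SAP 8.4 would select the earlier pre-dose value for that visit, and where the ED visit falls in no Table 1 window.

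**Cost:** one routine blood and urine sample and one set of vital signs per early leaver, at a visit already held and with tests the central laboratory already runs, plus a short amendment and a sentence in each of the two SAP sections.
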